2.2.2 Intranasal Delivery System Devices

The intranasal delivery device investigated in this study has been used in ongoing and previous studies at Wake Forest:

- 1) An investigational device (ViaNaseTM) developed by Kurve Technology (Bothell, WA) will be used in this study; the current device is identical to the model used in two studies approved by the Wake Forest IRB, SNIFF Long, IRB number 00023230 and [name] study of Intranasal Insulin and Post Stroke Cognition, IRB00029022. Typical spray bottle administration results in large droplets that penetrate only within the first 20% of the lower nasal cavity, and due to gravity and insufficient airflow, ~90% of the droplets wind up in the stomach. The ViaNaseTM device delivers a substance throughout the nasal cavity (to the olfactory region and paranasal sinuses), thereby maximizing access to nose-to-brain channels. This controlled particle dispersion (CPD) occurs because droplet size is adjusted according to the weight of the substance through an individually optimized droplet generator resulting in maximal vertical distribution.

3.0 PRELIMINARY STUDIES

A preliminary study examined the impact of 4-month INI administration using the ViaNase device (10 or 20 International Units bid vs. placebo) on the primary outcome measures of delayed story recall and the Dementia Severity Rating Scale (DSRS) as well as on measures of global cognition and function used in traditional AD clinical trials. In a subset of participants, effects on CSF AD biomarkers (A β 42 and tau/A β 42 ratio), and on cerebral metabolic rate of glucose utilization (CMRglc) assessed by F18FDG PET were also examined (Craft, Baker et al. 2012).

3.1 Participants

A total of 111 older adults were randomized in the study (Fig. 1). Data from 104 participants were analyzed.

Sample composition (aMCI, n=64; AD with MMSE >15, n=40), size, and diagnostic criteria were based on a previous study (Reger, Watson et al. 2008). Forty participants (15 placebo, 13 low dose insulin and 12 high dose insulin) completed the PET sub-study, and 23 participants (n=8 placebo and 15 insulin) completed the LP sub-study. Diagnoses were determined by expert physician and neuropsychologist consensus. Participants, caregivers, and all personnel involved in data collection were blinded to treatment assignment.

Groups did not differ in education, body mass index, MMSE, gender, diagnosis, cholinesterase inhibitor treatment, or apolipoprotein E (APOE) $\epsilon 4$ allele carriage (Table 1).

Figure 1 | Trial Enrollment Flow

[figure not shown]

Table 1 | Participant Characteristics

	Placebo (n=30)	Low Insulin (n=36)	High Insulin (n = 38)
Age (mean yrs, SEM)	74.9 (1.6)	72.8 (1.5)	69.9 (1.4)*
Education (mean yrs, SEM)	15.3 (0.6)	15.5 (0.5)	16.2 (0.5)
3MSE (mean, SEM)	84.2 (2.7)	83.7 (2.5)	84.3 (2.4)
BMI (mean kg/m ² , SEM)	27.4 (0.8)	26.7 (0.8)	26.9 (0.7)
Gender (%F/M)	43.3%/56.7%	38.9%/61.1%	47.4%/52.6%
AChEI Treatment (%No/Yes)	60%/40%	72.2%/27.8%	65.8%/34.2%
APOE- $\epsilon 4$ Carriers (%No/Yes)	55.2%/44.8%	50%/50%	57.9%/42.1%
Diagnosis (%MCI/AD)	70%/30%	55.6%/44.4%	60.5%/39.5%

*High dose<placebo, p<0.05

Participants in the high dose insulin group were younger than placebo-assigned participants ($p=0.02$), whereas no differences were observed between placebo and low dose insulin groups. Age was included as a covariate in all analyses.

3.2 Procedures

Participants were randomized to receive 10 International Units INI bid for a total daily dose of 20 International Units INI (n=36), 20 International Units INI bid for a total dose of 40 International Units (n=38) or placebo (saline bid, n=30) for 4 months. Participants were stratified by APOE- ϵ 4 carriage. Saline or insulin (Novolin R, Novo) was administered after breakfast and dinner with ViaNaseTM, an intranasal delivery system (Craft, Baker et al. 2012). Parallel versions of the cognitive protocol were administered at baseline, and months 2 and 4 of treatment. Co-primary outcome measures were delayed story recall and the DSRS which had previously demonstrated beneficial effects of insulin (Reger, Watson et al. 2008). Secondary measures included the AD Assessment Scale for Cognition (ADAS-Cog) (Reger, Watson et al. 2008), a test comprised of measures of memory, orientation, and language, with higher scores reflecting impairment ranging from 0 (best) to 70 (worst), and the ADCS-Activities of Daily Living scale (ADCS-ADL) (Galasko, Bennett et al. 1997). Baseline and post-treatment fasting CSF was analyzed for A β 42 and tau with multi-parameter bead-based immunoassay INNO-BIA AlzBio3 (Innogenetics NV). Resting PET images were obtained using a GE Advance PET scanner (GE Medical Systems, Milwaukee, WI) using a previously described protocol (Baker, Cross et al. 2011).

3.3 Safety and Compliance

Support persons supervised participants' intranasal administration. Blood glucose was measured daily for the first week and then weekly; no group changes were observed over the course of the study (Craft, Baker et al. 2012). Compliance was monitored by quantifying unused drug. Safety data were reviewed semi-annually by a Data and Safety Monitoring Board. Adverse event reporting followed standard guidelines.

[figure not shown]
3.4 Statistical Analyses

For the intent-to-treat (ITT) sample, co-primary (delayed story recall and DSRS) and secondary (ADAS-Cog and ADAS-ADL) scores were log transformed. Scores were first subjected to mixed model repeated ANCOVA including all treatment groups (placebo, low dose insulin or high dose insulin) as the between subjects factor, and time (baseline, month 2, month 4) as the repeated factor using the SAS v9.2 General Linear Models procedure. After a significant ($p<0.05$) time by treatment group interaction reflecting a different pattern of change, each of the two insulin groups was compared separately with the placebo group using repeated measures ANCOVAs. Effect sizes (Cohen's f^2) were calculated for all significant effects. Age was included as a covariate in all analyses. Diagnosis (aMCI or AD), gender, APOE- ϵ 4 carriage status (yes or no), baseline 3MSE score, and years of education were also included as covariates. Non-significant covariates were dropped from the model. Significant relationships with covariates were explored with Pearson correlation (continuous variables) or follow-up ANOVAs (class variables). Missing values were treated with multiple imputation (Rubin 1987). For exploratory CSF biomarker analyses, because only a subset of participants elected to undergo LP and no differences were observed between the two insulin dose arms, the groups were combined into a single insulin-treated group to maximize power. Biomarkers were analyzed with the repeated ANCOVA strategy described above and, due to the small sample size, exploratory Spearman correlations were conducted to examine relationships among changes in biomarkers and outcome measures. Only study completers underwent post-treatment FDG-PET. Pre and post treatment scans were co-registered within subject and anatomically standardized to Talairach and Tournoux stereotactic coordinates (Talairach and Tournoux 1988, Minoshima, Koeppe et al. 1994). Pixel intensity was normalized to pontine values (Minoshima, Frey et al. 1995). Interval regional CMRglc changes within groups were assessed using voxel-wise one-sample t statistics (pre-/post-treatment pair) and probability integral conversion to z scores (Worsley, Evans et al. 1992). Interval changes in regional CMRglc were then compared between 1) low insulin vs. placebo groups, and 2) high insulin vs. placebo groups. Based on the number of voxels and smoothness of the statistical map, a Type I error rate was controlled at 0.05 to account for multiple comparisons (Worsley, Evans et al. 1992). The resulting statistical maps were visualized in three-dimensional stereotactic surface projections.

3.5 Results: Cognitive and Functional Outcome Measures

The three groups did not differ at baseline on any outcome measure; change from baseline is represented in figures for ease of interpretation. A significant overall treatment group by time interaction was observed for primary outcome delayed story recall ($p=0.005$). Compared to placebo, the low dose group had improved delayed recall (Fig. 2A; treatment by time $p=0.02$, Cohen's $f^2=0.36$), whereas no effect was observed for the high dose group. Exploratory post-hoc analyses were then conducted to more closely examine the relationship of insulin dose to story recall, as this was a primary goal of this pilot clinical trial. Given findings that delayed recall may not be a sensitive measure for AD subjects due to increased variability and floor effects (Sano, Raman et al. 2011) we constructed a total story recall score (immediate and delayed), which showed improvement for the high-dose group (time by treatment interaction $p<0.05$, mean log total story recall change score with SEM = $-.15(.1)$ for placebo vs $.12 (.09)$ for the high dose group). A significant overall treatment by time interaction was observed for the other primary outcome measure, the DSRS ($p=0.008$). Compared with placebo, DSRS scores were preserved for both low and high dose groups (Fig. 2B; treatment by time $p=0.01$ and 0.01 , Cohen's $f^2=0.38$ and 0.41). For secondary measures, significant effects were observed for the ADAS-Cog (overall treatment by time interaction $p=0.004$). Both low and high insulin groups had less decline in cognition compared with placebo (Fig. 2C; treatment by time $p=0.04$ and $p=0.002$, Cohen's $f^2=0.27$ and $.40$). Treatment effects on the ADAS-Cog interacted with age; for the high dose insulin group, greater improvement (lowered score) tended to be associated with younger age ($r=.31$, $p=0.06$). For the ADCS-ADL, no overall effects of treatment on daily function were observed. However, a significant interaction with diagnosis was observed for this measure (overall treatment by time by diagnosis interaction $p=0.02$). Participants with AD receiving either dose of insulin had preserved function compared with placebo-assigned participants with AD who showed slight decline, whereas participants with aMCI showed no change regardless of treatment assignment (interactions for the participants with AD in low and high dose groups compared with placebo, $p=0.01$ and 0.02 , Cohen's $f=0.45$ and 0.43 ; Fig. 2D). Adjustment for APOE- $\epsilon 4$ status, baseline MMSE score, cholinesterase inhibitor treatment, gender, and education did not affect the pattern of any result.

Figure 2 | Change (Month 4-baseline) in log scores for (A) delayed story recall, (B) DSRS, (C) ADAS-Cog and (D) ADCS-ADL.

3.6 Results: AD Biomarkers

CSF A β 42, A β 40 and tau did not change for the placebo or insulin-treated groups as a whole. In exploratory analyses, however, for insulin-treated participants, increased CSF A β 42 concentrations were associated with improved delayed story recall and ADCS-ADL scores, whereas decreased A β 42 was associated with worse performance (Spearman rhos=.59, p=0.02 and .60, p=0.02). Similarly, decreased tau/A β 42 ratios over the 4-month study period correlated with improved delayed story recall and better daily function on both ADAS-ADL and DSRS for insulin-treated participants (Spearman rhos=-.52, p=0.05, -.50, p=0.07, and .53, p=0.05). No significant correlations were observed for the placebo group.

3.7 Results: FDG-PET CMRglc

Compared with placebo-assigned participants, the lower dose insulin group showed reduced progression of hypometabolism in bilateral frontal, right temporal, bilateral occipital, and right precuneus and cuneus regions over the 4-month treatment period (Fig. 3 and Table 2). The higher dose insulin group showed even greater treatment effects (higher Z scores) indicating less hypometabolism progression in most regions and in left parietal cortex.

Figure 3 | Areas of hypometabolism at baseline (scan 1) and month 4 (scan 2), along with changes in hypometabolism (time 2-time 1) within each group and differences in change between placebo and low or high insulin groups (nasal insulin-placebo). Hotter floors indicate areas of greater hypometabolism from time 1 to time 2, and from placebo to insulin groups.

[figure not shown]

Table 2 | Z scores and stereotactic coordinates for areas of reduced progression for low and high does insulin groups compared to placebo

	Z	Stereo Coordinates		
		x	y	z
Low Dose Insulin – Placebo				
Inferior occipital cortex (L)	4.3	19	-62	-7
Lateral temporo-occipital cortex (R)	3.9	-39	-80	2
Precuneus (R)	3.8	-3	-73	23
Superior temporal cortex (R)	3.7	-53	-24	2
Lateral occipital cortex (L)	3.5	6	-87	9
Orbital frontal cortex	3.2	-1	48	-16
High Dose Insulin - Placebo				
Orbital frontal cortex	5.8	1	23	-18
Inferior occipital cortex (L)	5.3	21	-64	-9
Inferior parietal cortex (L)	4.1	35	-40	47
Precuneus/Cuneus (R)	4.1	3	-80	18
Lateral occipital cortex (L)	3.7	26	-85	11
Medial fronto-parietal cortex (L)	3.7	10	-19	41
Caudate (R)	3.6	-12	3	20

Positive value on the x coordinate indicates the left hemisphere.

Positive value on the y coordinate indicates anterior brain.

Positive value on the z coordinate indicates superior brain.

3.8 Safety and Compliance

No treatment-related serious adverse events (SAEs) occurred during the study; most adverse events (AEs) were minor, such as mild rhinitis. AEs with an occurrence of >5% in any group are listed in Table 3. The total AE mean was higher for the low dose group compared with placebo (low dose mean total AEs with standard error=1.44±0.20, placebo =0.80±.22, p=0.04), with a similar trend for the high dose and placebo group comparison (high dose mean total AEs =1.21±0.16, placebo =0.80±.22, p=0.10). Mean compliance (number of completed doses) ranged from 95-97% and did not differ across groups.

Table 3 | Total number of adverse events and percent of sample for all events occurring for at least 5% of the participants in any treatment group.

	Placebo	Low Insulin	High Insulin
Total AEs	27/56.7%	55*/72.2%	51+68.4%
Dizziness	3/10%	3/8.3%	5/13.2%
Headache	1/3.3%	4/8.3%	2/5.3%
Nose bleed	0/0.0%	6/8.3%	3/2.6%
Rhinitis	1/3.3%	8/16.7%	4/7.9%
URI	2/6.7%	2/5.6%	1/2.6%
Fall	2/6.7%	1/2.8%	1/2.6%
Rash	2/6.7%	1/2.8%	2/2.6%
Other	16/46.7%	30/58.3%	33/60.5%

* Low Insulin Total AEs > Placebo, p<0.05

+High Insulin Total AEs > Placebo, p<0.10

3.9 Implications

These results suggest that adults with aMCI or AD may benefit from INI treatment. Compared with placebo, the lower dose of insulin improved delayed memory, and both insulin doses preserved caregiver-rated ability to carry out daily functions. General cognition as assessed with the ADAS-Cog, the primary outcome measure for the current trial, was also preserved by both doses of INI. In exploratory analyses, changes in CSF A β 42 and tau/A β 42 ratios were associated with cognitive and functional changes for insulin-treated participants. Placebo-assigned participants showed decreased CMRglc values in frontal, temporal, and parietal cortices as well as precuneus and cuneus over the 4-month period, whereas insulin-treated participants showed no decline. The longstanding FDG PET finding of posterior cingulate, precuneus and cuneus hypometabolism in AD has been hypothesized to be due to functional disconnection of the hippocampal formation, so enhanced metabolism and memory with INI may reflect enhanced hippocampal input to this region. Similarly there are strong connections between the posterior cingulate, precuneus, cuneus and prefrontal and superior temporal cortex (Cavanna and Trimble 2006), which may also be affected by INI. Finally, no treatment-related SAEs occurred. These promising results provide a strong rationale for the longer, larger, multi-site trial proposed in this application.

4.0 PRELIMINARY STUDY 2

A follow-up study has recently concluded and preliminary results have been analyzed.

Objectives: This study tested the effects of 40 International Units of intranasal insulin administered daily for 12 months, compared with placebo, on cognition, daily function and safety in adults with MCI or mild AD. Longer-term effects were examined in a six-month open-label extension offered to all participants. Safety and feasibility issues relating to the use of intranasal delivery devices were also evaluated. The trial is nearing completion; all participants have concluded the blinded phase.

Methods: Twenty-six sites enrolled 289 participants with MCI or mild AD in this randomized, double-blind, Phase II/III trial (NCT01767909). Adults 55 to 85 years of age with diagnoses of amnestic MCI or AD (National Institute on Aging-Alzheimer's Association criteria) with Mini-Mental State Exam (MMSE) scores >19, Clinical Dementia Ratings (CDR) of 0.5 or 1, and delayed Logical Memory scores within a specified education-adjusted range were eligible. Participants with diabetes requiring medication were excluded, as were participants who had used insulin within one year of the screening

visit. Participants were randomized on a 1:1 basis using a covariate-adaptive algorithm that weighted MMSE, apolipoprotein E-ε4 (APOE-ε4) allele carriage, study site, sex, and age based on previous work indicating these factors may impact treatment response. Participants received 40 International Units of insulin or insulin diluent placebo (Humulin R U-100 or insulin diluent, Eli Lilly, Indianapolis, USA) daily for 12 months. At the end of the 12-month blinded phase, all participants were offered open-label insulin treatment for 6 months. The primary outcome (Alzheimer's Disease Assessment Scale for Cognition-12/ADAS-Cog12) was administered at baseline and then at 3 month intervals. Secondary functional outcomes (Alzheimer's Disease Cooperative Study-Activities of Daily Living Scale for MCI; CDR Sum of Boxes) were assessed at 6 month intervals, as was a memory composite (Free and Cued Selective Reminding Test and Story Recall). Cerebrospinal fluid biomarkers (Aβ42 and Aβ42/tau ratio) and magnetic resonance imaging hippocampal and entorhinal cortex volumes were measured at baseline and after 12 months.

Device issues. Intranasal delivery device monitoring revealed no safety issues. However, for the first 49 participants, the delivery device had frequent malfunctions (i.e. failure to turn on) that impacted dosing reliability. At that time, a newly available device was introduced (Precision Olfactory Device/POD, Impel NeuroPharma, Seattle, USA) which was used by the remaining 240 participants with good reliability.

Results: Demographic characteristics of enrolled participants are presented in Table 1. Retention was excellent, with only 25 participants discontinuing treatment during the blinded phase, and 15 also discontinuing study visits during the blinded phase. Quarterly DSMB reviews did not detect any safety issues and approved unmodified continuation of the trial.

Data from the subgroup of participants who used the POD were analyzed separately from the ViaNase group. The primary analysis of the POD group showed was negative; no difference in ADAS-Cog12 scores were observed after 12 months of INI treatment compared with placebo (Fig.1). In contrast, analysis of the ViaNase group showed beneficial effects of insulin compared with placebo; the effect was significant at 6 months ($p<0.01$), and persisted at 12 months ($p=0.09$; Fig. 2).

Table 1. Baseline Participant Characteristics	
N (F/M)	289 (134 / 155)
Age (years)	70.95 ± 7.1
Diagnosis (MCI/AD)	105 / 184
MMSE	24.8 ± 2.7
Logical Memory	2.1 ± 2.7
APOE (ε4+/ε4-)	193 / 96

[figure not shown]
[figure not shown]

Fig. 1

Fig. 2

Implication: These results suggest that the two delivery devices may be providing different doses of insulin to the CNS. The ViaNase device results are consistent with multiple previous studies. The POD had not been used previously in clinical trials with insulin, and thus was relatively untested in terms of delivery efficacy, although modeling in organoid nasal cavities was conducted to verify that the target amount of insulin was dispersed to the target location in the nasal cavity. These divergent results can potentially be clarified by conducting a proof of concept study, in which insulin or placebo will be administered and then insulin in CSF will be measured 30 minutes after administration. Results 07-December-2020

IND #: 119232

of this proof of concept study will help confirm the delivery capabilities of the ViaNase device, information that is essential to the design of a future Phase III trial.

4.1 Rationale for Dosage Selection

The dosage selected (20 International Units INI) has been used in two prior studies with positive results as described above.

4.2 Rationale for Primary and Secondary Outcome Measures

Previous work demonstrates that following intranasal insulin administration, insulin levels are increased in the CSF, reflecting entry into the CNS, and with the greatest increases observed 30 minutes after administration (Born et al. *Nature Neuroscience*, 2002 Jun;5(6):514-6). The observation that CSF levels are increased following insulin administration with the ViaNase device will validate that insulin was delivered to the CNS and thus that the positive results for the ADAS-Cog12 for the POD cohort in the recent study are possibly due to its ability to successfully deliver insulin to the CNS.

Regarding secondary measures, in previous studies intranasal insulin acutely improved memory performance and affected CSF levels of AD biomarkers (Reger et al. 2008; Craft et al. 2012). Thus examining effects on these measures will provide supportive information about access to and efficacy in the CNS.

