2.2 Insulin as a Therapeutic Agent

The study uses insulin as a therapeutic agent and intranasal administration focusing on nose to brain transport as a mode of delivery. As reviewed above, insulin has pleiotropic effects on pathways implicated in AD pathogenesis. As such, augmenting CNS insulin is an alternative approach to AD therapy, in contrast to the majority of therapeutic approaches that focus on narrowly defined mechanisms such as acetylcholine modulation or amyloid accumulation. Restoring normal brain insulin levels in persons with AD may improve cognition and AD pathologic processes. Such an approach is possible with an intranasal administration technique.

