2.2.1 Intranasal Pathways to the CNS

Olfactory sensory neurons are directly exposed to the external environment in the upper nasal cavity while their axons extend through the cribriform plate to the olfactory bulb. Following intranasal administration, drugs can be directly transported to the CNS, bypassing the periphery. Several extraneuronal and intraneuronal pathways from the nasal cavity to the CNS are possible. The extraneuronal pathways appear to rely on bulk flow transport through perineural channels to the brain or CSF. In recent studies, labeled INI or a closely related peptide, insulin-like growth factor-I (IGF-I), were administered to rodents (Thorne, Pronk et al. 2004, Francis, Martinez et al. 2008). Within 30 minutes, signal was detected along olfactory and trigeminal channels, as well as in the hippocampus, amygdala and rostral and caudal cortex. An additional extracellular pathway was identified with quick access to the CSF after absorption into the submucosa along the olfactory nerve and cribriform plate (Born, Lange et al. 2002, Frey 2002, Thorne, Pronk et al. 2004). These extracellular pathways provide direct access to the CNS within minutes of intranasal administration. Additionally, an intraneuronal pathway delivers drugs to the CNS hours or days later (Broadwell and Balin 1985, Shipley 1985, Baker and Spencer 1986, Balin, Broadwell et al. 1986). Viruses and microorganisms (Fairbrother and Hurst 1930, Faber 1938, Bodian and Howe 1941), amino acids (Weiss and Holland 1967), and proteins (Kristensson and Olsson 1971, Shipley 1985, Thorne, Emory et al. 1995) can also enter the CNS via nasal routes. In particular, substances with lower molecular weights are more likely to be transported to the CNS along intranasal pathways (Sakane, Akizuki et al. 1995). Insulin's molecular weight of about 5800 g/mol makes it a good candidate for intranasal delivery. Animal studies show labeled uptake to hippocampus and rostral and caudal cortex following INI administration (Francis, Martinez et al. 2008). In a murine diabetes model, INI reduced brain atrophy, while increasing synaptic markers and activation of Akt, CREB, and GSK3 β . Memory enhancement was also observed on Water Maze and radial arm tasks (Francis, Martinez et al. 2008). Human functional and cognitive studies of INI also support insulin's transport to the CNS. INI treatment increases CSF insulin levels and induces changes in auditory-evoked brain potentials compared to placebo (Kern, Born et al. 1999). INI improves verbal memory

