
07-December-2020

IND #: 119232

acutely in persons with AD and aMCI without affecting plasma insulin or glucose levels at the dose included in the study (Reger, Watson et al. 2006). Regarding chronic effects, several studies reported that 2 months of daily insulin administration (160 International Units/day) significantly improves verbal memory in young healthy adults (Benedict, Hallschmid et al. 2004, Stockhorst, de Fries et al. 2004, Benedict, Kern et al. 2008, Hallschmid, Benedict et al. 2008, Stockhorst, de Fries et al. Submitted for publication). Finally, Section 3.0 presents results in a preliminary study in which insulin was administered to adults with AD or aMCI for 4 months.

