5.1 Study Population

A total of 30 adults who are cognitively normal or diagnosed with aMCI will be enrolled in this trial. We expect to enroll approximately 50% of participants from each group. To determine eligibility, all participants will undergo cognitive assessment, physical and neurological examination, ECG, clinical/safety laboratory assessment, and interviews of the participant and study partner conducted by the investigators and staff of the Clinical Core of the Wake Forest Alzheimer's Disease Research Center (ADRC).

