12.0 POTENTIAL RISKS

12.1 Safety of Intranasal Insulin

Safety issues pertaining to INI administration for the treatment of diabetes have been extensively explored for over two decades (Pontiroli, Alberetto et al. 1982). For diabetes treatment, absorption enhancers must be used to increase the transport of insulin across the nasal membrane to the periphery due to the fact that peripheral bioavailability of insulin without absorption enhancers is less than 1% (Illum 2002). A recent safety study of INI administration without absorption enhancers demonstrated no treatment induced changes in blood glucose levels, nasal airway patency, or transnasal pressure gradient (Kupila, Sipila et al. 2003). There are no known serious risks associated with INI without enhancers. A recent industry report raised the issue of rare but significant increases in lung cancer in smokers treated with inhaled insulin; six of 4740 patients taking inhaled insulin developed lung cancer compared with one of 4292 patients who received an active comparator (incidence per 100 patient years exposure, 0.13 vs 0.02). However, the inhaled insulin protocol used for diabetes treatment in this report included absorption enhancers to maximize delivery to lungs, whereas the nose-to-brain delivery device to be used in this study greatly minimizes lung delivery.

Regarding the risk of hypoglycemia, at least five peer reviewed human studies (Kern, Born et al. 1999, Born, Lange et al. 2002, Kupila, Sipila et al. 2003, Benedict, Hallschmid et al. 2004, Stockhorst, de Fries et al. Submitted for publication) and four preliminary studies (Reger, Watson et al. 2006, Reger, Watson et al. 2008, Reger, Watson et al. 2008) (Craft, Baker et al. 2012) revealed no change in blood glucose levels following intranasal insulin administration with doses that included 40 International Units 4 times daily for two months. There was one exception with the case of a single participant who experienced mild hypoglycemia (52 mg/dl) after skipping a meal and engaging in sustained vigorous exercise. In

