14.1 Humulin® R U-100 Insulin

Humulin® R U-100 (NDC: 0002-8215, Eli Lilly & Company) is a polypeptide hormone structurally identical to human insulin synthesized through rDNA technology in a special non-disease-producing laboratory strain of *Escherichia coli* bacteria. Humulin R U-100 has the empirical formula C₂₅₇H₃₈₃N₆₅O₇₇S₆ and a molecular weight of 5808 Da. Humulin R U-100 is a sterile, clear, aqueous, and colorless solution that contains human insulin (rDNA origin) 100 units/mL, glycerin 16 mg/mL and metacresol 2.5 mg/mL, endogenous zinc (approximately 0.015 mg/100 units) and water for injection. The pH is 7.0 to 7.8. Sodium hydroxide and/or hydrochloric acid may be added during manufacture to adjust the pH.

More information about the Humulin® R U-100 insulin, including risks, contraindication and adverse reactions can be found in the the US package insert (USPI).

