14.6 Intranasal Administration

Insulin or placebo will be administered with a ViaNase™ drug delivery device (Kurve Technology, Bothell, WA). ViaNase™ specifically targets olfactory delivery to maximize drug transport to the CNS. This device releases a metered insulin dose into a chamber covering the participant's nose. The insulin or placebo is then inhaled by breathing evenly over a specified period. This method allows administration of smaller particle sizes to increase deposition in the upper nasal cavity while minimizing transport to the lungs. A volume of about 0.7 mL of insulin or placebo will be administered each time.

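### The stated 20 units do not match about 0.7 mL of a 100 units/mL product, and Section 4.2 credits the positive earlier result to the wrong device

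*Combined protocol and SAP*

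**What the plan says.** **Amount given.** The synopsis lists 20 International Units of Humulin R U-100 or matching saline. The same 20 units appear in the primary aim (1.1), the dose rationale (4.1), the study overview (5.0), both dosing visits (7.2, 7.3) and the study drug section (14.0). Section 14.1 says the product "contains human insulin (rDNA origin) 100 units/mL". Section 14.5 says only that the study nurse puts the drug into the device chamber. Section 14.6 says "A volume of about 0.7 mL of insulin or placebo will be administered each time".

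**Background tied to the dose.** Section 2.2.1 reports that intranasal insulin improved verbal memory "acutely in persons with AD and aMCI without affecting plasma insulin or glucose levels at the dose included in the study". Section 12.1 adds that "peripheral bioavailability of insulin without absorption enhancers is less than 1" per cent.

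**What a positive result would mean.** Section 4.2 says that raised CSF levels "following insulin administration with the ViaNase device will validate that insulin was delivered to the CNS". The same sentence goes on to explain positive ADAS-Cog12 results in the POD cohort. Section 4.0 reports no ADAS-Cog12 difference with POD and a benefit with ViaNase, and 19.1 says the same. Section 5.0 compares insulin with placebo through the ViaNase device only.

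**The concern.** The trial asks whether a given amount of insulin, delivered by one device, raises CSF insulin at 30 minutes. If the amount cannot be read from the protocol, the primary result has no defined exposure. The dose rationale in 4.1, the statement in 2.2.1 about plasma insulin at the study's dose, and the safety background in 12.1 all assume a known quantity. A positive result could not be carried into the Phase III design that 4.0 has in mind without knowing which quantity produced it.

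The error in 4.2 matters because that section states how the primary outcome will be read. As written, a rise with ViaNase is offered as an explanation for a benefit that the protocol reports did not occur with POD.

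**Working it through.** **1. Inputs.** Stated dose 20 units (synopsis, 1.1, 4.1, 5.0, 7.2, 7.3, 14.0). Concentration 100 units/mL (14.1). Volume about 0.7 mL of insulin or placebo (14.6).

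**2. Units implied by the volume, undiluted.** Units = volume × concentration = 0.7 × 100 = 70. Ratio to the stated dose: 70 / 20 = 3.5.

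**3. Volume implied by the dose, undiluted.** Volume = dose / concentration = 20 / 100 = 0.2 mL.

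**4. Can the word about absorb the gap?** If it covers rounding to one decimal (my assumption: 0.65 to 0.75 mL), the undiluted amount is 65 to 75 units. No reasonable rounding reaches 20.

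**5. What would make the figures agree.** Holding 20 units and 0.7 mL, the solution given would have to be 20 / 0.7 = 28.6 units/mL, that is, diluted before loading. Alternatively, 0.7 mL might be a loaded volume of which only part is given, but 14.6 calls it the volume administered. Sections 14.5 and 14.6 describe neither arrangement. The calculation shows a missing or incorrect statement; it does not show which one.

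**6. Effect on the background.** The 12.1 ceiling of 1% corresponds to 0.01 × 20 = 0.2 units or 0.01 × 70 = 0.7 units. These are upper bounds, and the documents do not convert them to a plasma or CSF concentration. Section 12.1 also cites 40 units four times daily (4 × 40 = 160 a day) and 60 units once daily. A single 70-unit administration would exceed either single amount but not the 160-unit daily total. The 2.2.1 statement refers to the dose of this study, so it can be applied only once that dose is unambiguous.

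**7. The device sentence.** Set side by side:

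| Section | POD | ViaNase |
|---|---|---|
| 4.0 | Primary analysis negative at 12 months | Benefit at 6 months (p<0.01); p=0.09 at 12 months |
| 19.1 | Earlier results not replicated | Earlier results replicated |
| 4.2 | Positive ADAS-Cog12 results | Device whose CSF rise is to explain them |

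Sections 4.0 and 19.1 agree with each other, and 4.2 contradicts both.

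**8. What the design can say about POD.** The contrast in 5.0 is insulin against placebo, both given by ViaNase. No term in it involves POD, so no value of the result estimates a difference between devices.

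**The case against.** **Dilution may be documented elsewhere.** A pharmacy or device manual could specify preparation to 0.7 mL, and a fixed volume for insulin and saline would suit blinding. That is plausible, and it is why one should not infer that participants receive 70 units; the documents do not support that reading. It does not remove the inconsistency, because 14.6 says what is administered, 14.1 gives the strength, and the protocol has no step joining them.

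**The POD limit is already hedged.** Section 4.0 says only that the divergent results can potentially be clarified, and it confines the stated goal to the delivery capabilities of ViaNase. This is fair: the absence of a POD condition is a limit to state, not a design error.

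**A stronger reading about route.** The rationale in 2.2 is "intranasal administration focusing on nose to brain transport as a mode of delivery", and 2.2.1 says "drugs can be directly transported to the CNS, bypassing the periphery". A reader might infer that the trial claims to prove a nose-to-brain route and neglects plasma insulin. The documents do not support this. The aims and 4.2, 4.3, 11.1 and 19.1 claim only a CSF rise or delivery to the CNS, which the placebo comparison can address whatever the route. The route wording is background. Plasma insulin is collected at the lumbar puncture visits (7.2, 10.2, Table 4), and 11.0 plans treatment comparisons for plasma biomarkers. It is not a named outcome in the synopsis, and no text links it to reading the CSF result, but that is a matter of reporting detail.

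**Simulation would not add weight.** With the CSF effect held fixed, the primary test has the same power for every assumed route by construction, so such a figure says nothing about this trial.

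**Conclusion.** Two statements are wrong or incomplete as written. First, 20 units, 100 units/mL and about 0.7 mL cannot all describe an undiluted administration; the gap is 70 against 20 units, a factor of 3.5. This rests only on the protocol's own figures and on the absence of a dilution step in 14.5 and 14.6. Which figure should change is for the sponsor. Second, 4.2 reverses the device attribution given in 4.0 and 19.1.

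The primary comparison and its claim that insulin reached the CSF are not called into question. What is unsettled is the dose to which a positive result would apply. A rise with ViaNase also cannot show whether POD delivered less. Showing plasma insulin beside the CSF result would be useful but is not needed to correct an error.

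**What to change.** 1. Reconcile 14.1, 14.5 and 14.6 with the 20 units stated elsewhere. State the concentration loaded, the volume loaded, the volume administered and any preparation step, so that volume times concentration equals the stated dose. Check that 2.2.1, 4.1 and 12.1 then refer to the same quantity.
2. Correct the device attribution in 4.2 to agree with 4.0 and 19.1.
3. Add one sentence to 4.0 or 4.2 saying that, with no POD condition, the result does not show whether POD delivered less.
4. Optional: report the insulin-minus-saline difference in plasma insulin at the pre-puncture draw, on which 7.2 and 10.2 agree, with its 95% confidence interval beside the CSF result and without any claim about route. With 30 complete pairs, the half-width is 2.045 / √30 = 0.37 SD of the paired differences. A non-significant difference would therefore not exclude a moderate plasma rise.

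Items 1 to 3 are text corrections and need no new visit, sample or assay. Item 4 uses an assay already planned and falls under the plasma comparison in 11.0.
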